2. SYNOPSIS

Protocol Number: XSGP-304	
G-PEN (GLUCAGON INJECTION) COMPARED TO GLUCAGEN® HYPOKIT® (GLUCAGON) FOR INDUCED HYPOGLYCEMIA RESCUE IN ADULTS WITH T1D: A PHASE 3 MULTI-CENTER, RANDOMIZED, CONTROLLED, SINGLE BLIND, 2-WAY CROSSOVER STUDY TO EVALUATE EFFICACY AND SAFETY	
IND:	115091
EudraCT Number:	2018-002661-19
Project phase:	Phase 3
Compounds:	Xeris G-Pen (glucagon injection) Novo GlucaGen® Hypokit® (glucagon for injection)
Objectives:	
The primary objective of this study is to demonstrate that G-Pen 1 mg (test) is not inferior to GlucaGen Hypokit (glucagon, Novo Nordisk) 1 mg (reference), in Type 1 diabetic (T1D) subjects in a state of insulin-induced hypoglycemia.
 
The secondary objective of this study is to evaluate the safety and tolerability of G-Pen 1 mg versus GlucaGen Hypokit 1 mg in the study population.

Endpoints:	
The study objectives will be assessed by the comparison of the two study drugs for the following primary and secondary endpoints:
 
Primary: For the primary endpoint, groups will be compared for rates of achieving a positive plasma glucose response, defined as either a plasma glucose concentration > 70 mg/dL (> 3.88 mmol/L) or an increase in plasma glucose concentration > 20 mg/dL (>1.11 mmol/L) within 30 minutes of study drug injection.
 
Secondary: For the secondary endpoints, groups will be compared based on each of the following:
 
1. Rate of achieving a plasma glucose concentration > 70 mg/dL (> 3.88 mmol/L) within 30 minutes from injection of study drug.2. Rate of achieving an increase in plasma glucose concentration \geq 20 mg/dL (\geq1.11 mmol/L) within 30 minutes from injection of study drug.3. Rates of positive symptomatic response, defined as relief of neuroglycopenic symptoms within 30 minutes from a decision to dose.4. Rates of positive treatment response, defined as exhibiting either a positive plasma glucose response or a positive symptomatic response.5. Time to a positive plasma glucose response from injection of study drug.

	
 6. Time to administer study drug from a decision to dose. 7. Pharmacodynamic (PD) characteristics of mean plasma glucose concentration (0 to 90 minutes post-dose), maximum observed concentration (C_{max}), time to maximum observed concentration (t_{max}), area under the concentration versus time curve from time 0 to 90 minutes ($AUC_{(0-90)}$), and area under the concentration versus time curve from time 0 to 180 minutes ($AUC_{(0-180)}$). 8. Time to (a) initial relief and (b) complete resolution of autonomic and neuroglycopenic symptoms of hypoglycemia from a decision to dose. 9. Time to resolution of the overall feeling of hypoglycemia from a decision to dose. 10. Safety endpoints, including: adverse event (AE)/serious adverse event (SAE) rates, and changes in vital signs, laboratory variables, and physical exam/electrocardiogram (ECG) findings. 11. Tolerability endpoints, including: Draize scale scores for injection site erythema and edema as assessed by the investigator, and injection site discomfort and duration as assessed by subject questionnaire responses.
Study design:	This is a multi-center, randomized, active-controlled, single-blind, two-way crossover efficacy and safety inpatient study in adult subjects with T1D. The study will involve two daytime visits at a clinical research center (CRC) or comparable setting, scheduled 7 to 28 days apart. Subjects will be randomly assigned to receive G-Pen glucagon 1 mg during one period and GlucaGen Hypokit 1 mg during the other period.
Study location:	Approximately 8 clinical research centers in North America and Europe.
Study duration:	The estimated duration of study participation for each individual subject is approximately 4 weeks. The estimated duration of the entire study is 8 months.
Sample size:	It is anticipated that approximately 200 subjects will be screened for this study to achieve 122 randomized subjects and a goal of 111 subjects who are evaluable for treatment both periods.
Subjects:	The study will include male and female subjects with T1D between the ages of 18 and 75 years, inclusive, at Screening.
Inclusion Criteria:	
 1. Males and females diagnosed with T1D for at least 24 months. Women of childbearing potential require a negative urine pregnancy test and must use medically accepted contraception throughout the study and for 7 days after the last dose of study drug. Nursing mothers will be allowed to participate in the study. However, breast feeding during the inpatient study visits (Visits 2 and 3) and for 48 hours after each dose of study drug is not allowed. 2. Current usage of daily insulin treatment that includes having an assigned “correction factor” for managing hyperglycemia.

3. Age 18 to 75 years, inclusive.
4. Random serum C-peptide concentration < 0.6 ng/mL.
5. Willingness to follow all study procedures, including attending all clinic visits.
6. Subject has provided informed consent as evidenced by a signed and dated informed consent form (ICF) completed before any trial-related activities occur.

Exclusion Criteria:

1. Pregnancy
2. Glycated hemoglobin (HbA1c) > 10% at Screening.
3. Body mass index (BMI) > 40 kg/m².
4. Renal insufficiency (serum creatinine greater than 3.0 mg/dL) or Stage 2 or greater kidney failure.
5. Serum alanine aminotransferase (ALT) or aspartate aminotransferase (AST) equal to or greater than 3 times the upper limit of normal.
6. Hepatic synthetic insufficiency as defined as a serum albumin of less than 3.0 g/dL.
7. Hematocrit ≤ 30%.
8. Blood pressure (BP) readings at Screening where systolic blood pressure (SBP) < 90 or > 150 mm Hg, and diastolic blood pressure (DBP) < 50 or > 100 mm Hg.
9. Clinically significant ECG abnormalities.
10. Use of total insulin dose per day > 2 U/kg.
11. Inadequate venous access.
12. Congestive heart failure, New York Heart Association (NYHA) class II, III or IV.
13. History of myocardial infarction, unstable angina, or revascularization within the past 6 months.
14. History of a cerebrovascular accident or with major neurological deficits.
15. Active malignancy within 5 years from Screening, except basal cell or squamous cell skin cancers. Any history of breast cancer or malignant melanoma will be exclusionary.
16. Major surgical operation within 30 days prior to Screening.
17. History of or current seizure disorder (other than with suspect or documented hypoglycemia).
18. Current bleeding disorder, treatment with warfarin, or platelet count below 50×10^9 per liter.
19. History of pheochromocytoma or disorder with increased risk of pheochromocytoma (multiple endocrine neoplasia type 2 [MEN 2], neurofibromatosis, or Von Hippel-Lindau disease).
20. History of insulinoma.
21. History of allergies to glucagon or glucagon-like products, or any history of significant hypersensitivity to glucagon or any related products or to any of the excipients (dimethyl sulfoxide [DMSO] and trehalose) in the investigational formulation.

22. History of glycogen storage disease.
23. Subject tests positive for human immunodeficiency virus [HIV], hepatitis C virus [HCV], or hepatitis B virus [HBV] infection (hepatitis B surface antigen positive [HBsAg+]) at Screening.
24. Active substance or alcohol abuse (more than 21 drinks per week for male subjects or 14 drinks per week for female subject).
25. Administration of glucagon within 7 days of Screening.
26. Participation in other studies involving administration of an investigational drug or device within 30 days or 5 half-lives, whichever is longer, before Screening for the current study and during participation in the current study.
27. Any other reason the Investigator deems exclusionary.

Study Methods:

Subjects will complete the screening procedures to determine eligibility up to 30 days before enrollment into the treatment period and administration of study drug. Subjects not meeting eligibility criteria may be rescreened 30-days after an initial screen failure. A single re-screen is permitted, and this re-screen is only permissible if the reason for the prior screen failure was for laboratory measurements. Blood for clinical laboratory tests can be redrawn after a 30-day wait; however, other screening procedures do NOT need to be repeated. If the new clinical laboratory test results meet eligibility, the subject may be dosed. Otherwise, the subject is not eligible for dosing or further re-screening.

The evening prior to each inpatient study visit, subjects with confirmed plasma glucose not greater than 350 mg/dL (19.44 mmol/L) will be admitted for an overnight stay between 6 and 8 pm. Subjects will be provided a standardized dinner and will continue their usual insulin regimen per PI discretion. At the Investigator's discretion, subjects may receive a standardized snack before midnight the day before treatment.

Subjects will be instructed to fast after midnight. If site staffing allows for appropriate oversight, an intravenous (IV) catheter will be placed, and maintenance fluids will be administered. Otherwise, the subject's own infusion pump will be used overnight. The subject's plasma glucose will be monitored overnight, and glucose (IV or oral tablets) and/or insulin (IV or subcutaneous [SC]) will be administered as necessary to maintain plasma glucose within a recommended target range of 80 to 150 mg/dL (4.44 to 8.34 mmol/L).

Overnight glucose measurements outside of this recommended range will not be considered protocol deviations. At a minimum, glucose will be assessed by BGM or YSI (not CGM) at midnight, 3 am, and 6 am, with ± 30 minutes for these measurements, which will be entered into the EDC.

Subjects will continue to fast the morning of the procedure and an IV catheter for blood sampling will be inserted, ideally in the antecubital fossa of the arm. The hand used for blood sampling will be kept warm by use of a heated-hand box to increase blood flow and achieve "arterialized" samples. Subjects will be kept supine and covered under a blanket to maintain warmth.

The subject will be eligible to begin the baseline euglycemic steady state period when their plasma glucose is confirmed to be within the range of 70 to 270 mg/dL (3.89 to 15.0 mmol/L). IV insulin will be administered to maintain the plasma glucose within the range of 75 to 115 mg/dL (4.17 to 6.38 mmol/L) for 30 minutes. If the plasma glucose has been maintained within the range of 75 to 115 mg/dL (4.17 to 6.38 mmol/L) for at least 30 minutes, and the insulin infusion rate varies no more than $\pm 20\%$, the induction procedure may commence.

Eligible subjects will enter a state of insulin-induced hypoglycemia in a gradual and controlled fashion, through a monitored, standardized induction protocol.

During the baseline phase, plasma glucose measurements will be taken every 15 minutes. During the induction phase, plasma glucose measurements will be taken every 10 minutes while glucose is > 80.0 mg/dL (> 4.44 mmol/L) and at 5-minute intervals once plasma glucose is ≤ 80.0 mg/dL (≤ 4.44 mmol/L).

Once the initial plasma glucose measurement < 54.0 mg/dL (< 2.78 mmol/L) is achieved, the IV insulin infusion will be returned to the rate established at the end of the baseline euglycemia steady state period. After 5 minutes, the IV insulin infusion will be stopped, and a confirmatory plasma glucose reading will be taken to determine whether a hypoglycemic steady state has been reached, which is defined as a plasma glucose value ≥ 42 mg/dL (≥ 2.33 mmol/L) and < 54 mg/dL (< 2.78 mmol/L) with an 8-minute linearly extrapolated value for plasma glucose ≥ 42 mg/dL (≥ 2.33 mmol/L).

If the subject is not in a hypoglycemic steady state, plasma glucose should be rechecked at up to two subsequent 5-minute intervals. If the second or third confirmatory glucose is ≥ 42 mg/dL (≥ 2.33 mmol/L) and < 54 mg/dL (< 2.78 mmol/L) with an 8-minute linearly extrapolated value for plasma glucose ≥ 42 mg/dL (≥ 2.33 mmol/L), the subject will be deemed to be within a hypoglycemic steady state.

After the third confirmatory reading, if plasma glucose is < 42 mg/dL (< 2.33 mmol/L), the procedure will be terminated, study glucagon will NOT be administered, and the visit will be rescheduled after a minimum 3-day wait.

If plasma glucose is > 54 mg/dL (> 2.78 mmol/L) at any of the 3 confirmatory readings, IV insulin will be restarted at the rate used prior to the initial plasma glucose < 54 mg/dL being obtained.

When a state of stabilized insulin-induced hypoglycemia is verified, subjects will be administered the randomly assigned dose of either G-Pen glucagon 1 mg SC or GlucaGen Hypokit 1 mg SC to the abdomen, around the umbilicus at a 90° angle to the skin.

Study drug will not be prepared ahead of time. Rather, preparation of glucagon for administration will begin once the confirmatory plasma glucose reading is obtained, i.e., upon a “decision to dose.”

After administration of study drug, plasma glucose will be monitored at 5-minute intervals for 90 minutes, and afterwards every 30 minutes through 180 minutes posttreatment.

The induction procedure may elicit symptoms of hypoglycemia. Therefore, subjects will complete a questionnaire regarding hypoglycemia symptoms at the start of the hypoglycemia induction period and periodically through 180 minutes posttreatment.

After 180 minutes posttreatment, subjects will resume insulin pump therapy, if applicable, and will be given a meal. Subject may be discharged after 180 minutes posttreatment if their plasma glucose is > 100 mg/dL (5.56 mmol/L) and if medically stable. At the Investigator’s discretion, subjects’ prescribed insulin regimen can be restarted, or the meal can be given sooner, but not earlier than 90 minutes post-glucagon treatment, to prevent hyperglycemia or rebound hypoglycemia.

After a wash-out period of 7 to 28 days, subjects will return to the CRC and the study procedures will be repeated with each subject crossed over to the other treatment. After study-related procedures are performed on each of the treatment days, subjects will be discharged. A Follow-Up Visit will be

XSGP-304 Clinical Protocol
G-Pen (glucagon injection)

	
conducted 2 to 7 days after administration of the final dose of study drug as a safety check.
 
Tolerability will be assessed by comparing AE reports between the G-Pen and GlucaGen Hypokit treatment groups. In addition, at the end of each treatment period the subjects will complete questionnaires to assess injection site discomfort, and the Investigator will use a modified Draize scale to evaluate the injection sites after each administration.

Data management and statistical analysis:	
Data will be entered into an electronic Case Report Form (eCRF) by the study site personnel. Data will be monitored at on-site visits by Xeris personnel or by a contract research organization (CRO) delegated by Xeris. A stand-alone Statistical Analysis Plan (SAP) will be written to detail all protocol specified analyses. The SAP will take precedence over the protocol. The primary endpoint will be analyzed using an exact test procedure based on the conditional distribution for a maximum clinically acceptable non-inferior margin of $\leq 5\%$.

Sample Size Determination:	
For the primary analysis, a failure is recorded if the subject's plasma glucose fails to reach a concentration >70 mg/dL (>3.88 mmol/L) and fails to increase by at least 20.0 mg/dL (1.11 mmol/L) within 30 minutes of the decision to administer the dose of glucagon. The determination of a constant clinically non-inferior margin for the cure rate difference is generally difficult in practice for a number of reasons. To alleviate this concern, it has been recommended to use an Odds Ratio of success rates for estimation because the corresponding clinically non-inferior margin on the difference scale is getting small when the underlying success rate becomes large and close to 1. In this study, it is expected that the subject's recovery (success rate) will be high and approaching 100%. Since this is a cross-over design and each subject will serve as his/her control, power is improved.
 
The sample size was derived for 80% power of detecting non-inferiority with respect to the Odds Ratio of subject recovery rates at an alpha of 0.025 under a cross-over design. Based on an underlying Odds Ratio of 1.0, and failure rates of 0.2 versus 0.25, 111 subjects are required for the study. With an anticipated 10% drop-out rate, the total sample size for the study is 122 randomized subjects.

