The combination of one or more IV bolus doses of insulin along with continuous IV infusion of insulin will be used to gradually decrease a subject's plasma glucose to a target < 54.0 mg/dL (< 3 mmol/L). As per Section 11.2, all plasma glucose levels will be based on the average of two readings taken via YSI glucose analyzer at each time point. Plasma glucose measurements will be taken every 10 ± 5 minutes while glucose is > 65.0 mg/dL (> 3.61 mmol/L) and every 5 ± 2 minutes once plasma glucose is ≤ 65.0 mg/dL (≤ 3.61 mmol/L).

Once the initial plasma glucose measurement < 54.0 mg/dL (< 3 mmol/L) is achieved, the IV insulin infusion will be returned to the rate established at the end of the baseline euglycemia steady state period. After 5 minutes, the IV insulin infusion will be stopped, and up to three confirmatory plasma glucose readings will be taken at subsequent 5-minute intervals to determine whether a hypoglycemic steady state has been reached, which is defined as a confirmatory plasma glucose value ≥ 42 mg/dL (≥ 2.33 mmol/L) and < 54 mg/dL (< 3 mmol/L) with an 8-minute linearly extrapolated value for plasma glucose ≥ 42 mg/dL (≥ 2.33 mmol/L).

If a hypoglycemic steady state is not documented after any of three confirmatory readings, and plasma glucose is < 42 mg/dL (< 2.33 mmol/L) after the third confirmatory reading, the procedure will be terminated, study glucagon will NOT be administered, and the visit will be rescheduled after a minimum 3-day wait. At the Investigator's discretion, the subject should be treated with IV glucose or oral carbohydrates, it should be verified that the subject achieved a euglycemic state and is medically stable prior to discharge.

If plasma glucose is > 54 mg/dL (> 3 mmol/L) at any of the 3 confirmatory readings, IV insulin will be restarted at the 120% of the rate used prior to the initial plasma glucose < 54 mg/dL being obtained.

If a hypoglycemic state is verified by either the first, second, or third confirmatory reading, the subject will be eligible to receive either G-Pen or GlucaGen Hypokit in one of the randomized treatment sequences shown in Table 3. The time of the Investigator's "decision to dose" will be documented.

Table 3 Randomized Treatment Sequence

Treatment Sequence	Dose 1	Dose 2
1	G-Pen 1 mg	Novo GlucaGen Hypokit 1 mg
2	Novo GlucaGen Hypokit 1 mg	G-Pen 1 mg

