7.2. Hypoglycemia Induction Procedure and Justification

The most commonly used hypoglycemia insulin induction method cited in the literature [Nerموen] involves constant insulin infusion rates many-fold above normal basal infusion rates. As hepatic glucose production is determined by the glucagon to insulin ratio, this procedure may not create realistic circumstances for evaluating the effectiveness of glucagon in raising blood glucose. A predecessor study (XSGP-301), therefore, utilized a comparatively lower rate of insulin infusion at 1 to 2 times the normal basal rate, combined with push of an IV bolus dose of insulin derived from the subject's own self-reported glucose correction factor. About 30% of the procedures performed in Study XSGP-301 resulted in plasma glucose < 40 mg/dL (< 2.22 mmol/L). To get more precision in achieving a steady state of plasma glucose below 50 mg/dL (2.78 mmol/L), individual procedure data from the Study XSGP-301 were fitted to a model of insulin action allowing identification of opportunities for algorithm enhancements. The algorithm was modified accordingly and tested in the model of the procedures representing a broad spectrum of subjects, including the two extremes of insulin sensitivity that were associated with low plasma glucose in Study XSGP-303. The algorithm was further refined for use in the current study based on experiences in the XSGP-303 trial.

Hypoglycemia Induction Procedure

The evening before treatments subjects will be admitted to the CRC and follow the procedures described in Table 5.

Baseline Euglycemic Steady State

Prior to starting the hypoglycemia induction procedure, the subject must have stable plasma glucose for at least 30 minutes at 95 ± 20 mg/dL (75 to 115 mg/dL [4.17 to 6.38 mmol/L]) and a stable IV insulin infusion rate varying no more than $\pm 20\%$ during which plasma glucose must be measured at least every 15 ± 2 minutes.

Induction Start

For the induction, the starting plasma glucose level will be determined as the average of the last three YSI measurements taken during the baseline steady state period (i.e., start of baseline, next after 15 minutes, end of baseline after 30-minute baseline confirmation period). The following procedures will then be performed:

1. Subjects will continue the IV insulin infusion at the final rate of the baseline euglycemic steady state.
2. Subjects then will be given an initial IV bolus push dose of regular insulin diluted in saline:

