 - a. The dose will be calculated as 75% of the dose estimated to reduce plasma glucose from the subject's starting plasma glucose level to 54 mg/dL (3 mmol/L) based on the subject's self-reported glucose correction factor. This dose will be referred to as "1 bolus (i.e., full bolus dose)" subsequently. The Investigator may use discretion to decrease the amount of the calculated bolus dose based upon the subject's insulin sensitivity factor. However, the Investigator is not allowed to increase the amount of the bolus dose.
 - b. Plasma glucose will be measured every 5 to 10 minutes, depending on the current plasma glucose value (see [Table 4](#)).
 - c. The first insulin adjustment will be made no earlier than 20 minutes after the initial bolus but will otherwise follow the directions for insulin adjustments shown in [Table 4](#).

The Investigator may override the insulin dosing algorithm at their discretion. Note: investigator does not have discretion to give bolus doses once plasma glucose is 65 mg/dL (3.3 mmol/L) or less (see numbers 3.b.i and 4.b.i below).

When plasma glucose is > 80 mg/dL (> 4.44 mmol/L), insulin adjustments should not be made more frequently than every 10 minutes. When plasma glucose is ≤ 80 mg/dL (≤ 4.44 mmol/L), the minimum time between adjustments to decrease, terminate or re-start insulin is either 10 or 5 minutes, as indicated in [Table 4](#).

1. While plasma glucose is > 80 mg/dL (> 4.4 mM/L):
 - a. Measure plasma glucose every 10 minutes.
 - b. When 10 minutes have passed from the last insulin dose adjustment:
 - i. Bolus: If the rate of plasma glucose decrease is < 0.15 mg/dL·min (< 0.01 mM/min), then an additional 1 bolus (full bolus dose) should be administered.

- ii. Infusion Rate: If the rate of plasma glucose decrease is $< 0.5 \text{ mg/dL}\cdot\text{min}$ ($< 0.03 \text{ mM/min}$), then the insulin infusion rate should be increased by 20%.
 2. While plasma glucose is 66 to 80 mg/dL (3.66-4.4 mM/L):
 - a. Measure plasma glucose every 5 minutes.
 - b. When 10 minutes have passed from the last insulin dose adjustment:
 - i. Bolus: If the rate of plasma glucose decrease is $< 0.15 \text{ mg/dL}\cdot\text{min}$ ($< 0.01 \text{ mM/min}$), then an additional 1/2 bolus (half-bolus dose) should be administered.
 - ii. Infusion Rate:
 - 1) If the rate of plasma glucose decrease is $< 0.33 \text{ mg/dL}\cdot\text{min}$ ($< 0.02 \text{ mM/min}$), then the insulin infusion rate should be increased by 20%.

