 - 2) If the rate of plasma glucose decrease is $> 0.5 \text{ mg/dL}\cdot\text{min}$ ($> 0.03 \text{ mM/min}$), then the insulin infusion rate should be decreased by 20%.
 3. While plasma glucose is 61 to 65 mg/dL (3.39 to 3.61 mM):
 - a. Measure plasma glucose at least every 5 minutes.
 - b. When 10 minutes have passed from the last insulin dose adjustment:
 - i. Bolus: not allowed.
 - ii. Infusion Rate:
 - 1) If the rate of plasma glucose decrease is $< 0.25 \text{ mg/dL}\cdot\text{min}$ ($< 0.01 \text{ mM/min}$), then the insulin infusion rate should be increased by 20%.
 - 2) If the rate of plasma glucose decrease is $> 0.33 \text{ mg/dL}\cdot\text{min}$ ($> 0.02 \text{ mM/min}$), then the insulin infusion rate should be decreased by 20%.
 4. While plasma glucose is 54 to 60 mg/dL (3 to 3.33 mM):
 - a. Measure plasma glucose at least every 5 minutes.
 - b. When 10 minutes have passed from last insulin adjustment:
 - i. Bolus: not allowed.
 - ii. Infusion Rate:
 - 1) If the rate of plasma glucose decrease is $< 0.15 \text{ mg/dL}\cdot\text{min}$ ($< 0.008 \text{ mM/min}$), then the insulin infusion rate should be:
 - a. Increased by 20%, or

- b. Set at 120% of the previous rate if the infusion was previously set at the baseline rate or decreased by 50%.
Note: This escalation in rate can be performed every 5 minutes until the rate of decrease is $> 0.15 \text{ mg/dL}\cdot\text{hr}$ ($> 0.008 \text{ mM/hr}$)
 - 3) If the rate of plasma glucose decrease is greater than 0.25 up to 0.33 $\text{mg/dL}\cdot\text{min}$ ($>0.014 - 0.02 \text{ mM/min}$), then the insulin infusion rate should be decreased 20%.
 - 4) If the rate of plasma glucose decrease is greater than 0.33 up to 0.50 $\text{mg/dL}\cdot\text{min}$ ($>0.002 - 0.03 \text{ mM/min}$), then the insulin infusion rate should be decreased 50%.
 - 5) If the rate of plasma glucose decrease is $> 0.5 \text{ mg/dL}\cdot\text{min}$ ($> 0.03 \text{ mM/min}$), then the insulin infusion rate should be stopped. After 5 minutes, the insulin infusion should be restarted at the rate used at the end of the baseline period.
5. If the plasma glucose is $< 54 \text{ mg/dL}$ ($< 3 \text{ mM}$), then the IV insulin infusion should be returned to the baseline insulin infusion rate used at the end of the baseline period for 5 minutes, and then stopped.

Induction Termination

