RUN-IN 1 and RUN-IN 2 analysis phases will include all interventions before dose injections, thereof:

- EUGLYCEMIC BASELINE 1 / 2.

The Euglycemic Baseline phase will be determined as time interval which starts from last 30 minutes of the baseline euglycemic steady state period, covering at least 3 scheduled consecutive plasma measurements in the target range at 0, 15, and 30 minutes used to confirm euglycemic steady state; and stops just before hypoglycemia induction with IV bolus push dose.

Euglycemic Baseline (1 and 2): to determine for the Hypoglycemia Symptoms Assessment scheduled at the end of this phase just before the IV bolus push dose of insulin, will serve as baseline to determine hypoglycemia symptoms relief and/or resolution within Treatment Period (1 and 2). If more than one assessment is performed in this time interval, then the last assessment of each hypoglycemia symptom or score will be selected for use as the baseline.

- HYPOGLYCEMIA INDUCTION (1 and 2). During the induction procedure the subject will enter a state of hypoglycemia through the administration of regular insulin diluted in normal saline within a controlled and monitored setting.

Hypoglycemic steady state (1 and 2): for Treatment Period (1 and 2) is confirmed if:

- penultimate plasma glucose measurement during hypoglycemia induction is < 54.0 mg/dL (< 2.78 mmol/L);
- last plasma glucose measurement during hypoglycemia induction is ≥ 42 mg/dL (≥ 2.33 mmol/L) and < 54 mg/dL (< 2.78 mmol/L); and
- 8-minute linearly extrapolated value from two last measurements of plasma glucose is ≥ 42 mg/dL (≥ 2.33 mmol/L).

Hypoglycemic Baseline (1 and 2). If the subject achieved hypoglycemic steady state then from the last of the last two plasma glucose readings during hypoglycemia induction to time of study drug administration will be defined as Hypoglycemic Baseline for the corresponding treatment period and will serve as baseline for the Primary Endpoint and Secondary Endpoints related to pharmacokinetic and pharmacodynamic characteristics within Treatment Period (1 and 2).

Assessments and Adverse Events with onset in TREATMENT PERIOD 1 or TREATMENT PERIOD 2 will be attributed to the actual treatment and analyzed respectively. Adverse

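### Insulin-induction thresholds are misprinted: 54 mg/dL appears as 2.78 mmol/L (should be 3.00), three other unit pairs and one time unit are wrong, and the restart and sampling texts disagree

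*Protocol*

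**What the plan says.** **The 54 mg/dL threshold.** In the Protocol synopsis (Study Methods) the first low reading is described as "Once the initial plasma glucose measurement < 54.0 mg/dL (< 2.78 mmol/L) is achieved", and the restart rule is "If plasma glucose is > 54 mg/dL (> 2.78 mmol/L) at any of the 3 confirmatory readings, IV insulin will be restarted". Both synopsis sentences defining the hypoglycemic steady state use the same pair, making four occurrences. SAP 5.2 uses it twice in its analysis definition of steady state, starting with "penultimate plasma glucose measurement during hypoglycemia induction is < 54.0 mg/dL (< 2.78 mmol/L". Protocol 7.1 has instead "Once the initial plasma glucose measurement < 54.0 mg/dL (< 3 mmol/L) is achieved", and 3 mmol/L also stands in Protocol 7.2, 10.2.1.2, Tables 4 and 8, and SAP 4.1 and 6.3. Protocol 7.2 shows where 2.78 belongs when it describes earlier work on the algorithm: "steady state of plasma glucose below 50 mg/dL (2.78 mmol/L".

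**The bolus bar.** A note in Protocol 7.2 reads "investigator does not have discretion to give bolus doses once plasma glucose is 65 mg/dL (3.3 mmol/L) or less". The algorithm items below it forbid a bolus in two bands with correct units: "While plasma glucose is 61 to 65 mg/dL (3.39 to 3.61 mM" (item 3) and "While plasma glucose is 54 to 60 mg/dL (3 to 3.33 mM" (item 4).

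**The other items.**
- Protocol 7.1 twice gives the euglycemic upper limit of 115 mg/dL as 6.83 mmol/L. The synopsis, 7.2, 10.2.1.2 and Table 8 give 6.38.
- Protocol 7.2 item 4 prints 0.002 mM/min beside 0.33 mg/dL·min. Table 4 has 0.02.
- In the 54 to 60 mg/dL band, 7.2 and Table 4 both trigger escalation of the infusion below 0.15 mg/dL per minute but end it above 0.15 mg/dL per hour.
- After a confirmatory reading above 54 mg/dL, the synopsis restarts insulin at the previous rate, whereas 7.1 uses 120% of it. Section 10.2.1.2 refers to Table 4, whose 54 to 60 mg/dL row is compatible with 120%.
- The move to 5-minute sampling is at 80 mg/dL in the synopsis, 7.2 and Table 4, but at 65 mg/dL in 7.1.

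**The concern.** These numbers decide when IV insulin is started, cut or stopped and when a subject may be dosed. Protocol 11.2 lets sites enter glucose in either unit, so a site may legitimately work from the mmol/L figures.

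For such a site the synopsis and the body of the protocol can order opposite actions on the same reading. Suppose the initial reading was below 2.78 mmol/L and the first confirmatory reading is 2.85. The synopsis restarts insulin. Under 7.1 and 10.2.1.2 the reading is inside the dosing range and, because glucose is rising, the 8-minute extrapolation is met as well, so the subject is eligible for study glucagon.

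The per-hour stop, the restart rate and the sampling switch affect sites in either unit.

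**Working it through.** **Inputs.** The factor is f = 18.0182 mg/dL per mmol/L (SAP 7.3). Reference pairs come from Protocol Table 8 (50.0 = 2.78, 54.0 = 3.00, 65.0 = 3.61, 115.0 = 6.38), and the rate pair from Table 4.

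**Check of the method.** Dividing by f reproduces the Table 8 rows at issue: 50/f = 2.775, 54/f = 2.997, 65/f = 3.607, 115/f = 6.382. Using 18.0 instead changes none of the conclusions.

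**Printed pairs against computed values.**

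| Where | Printed pair | Correct value | Printed value in mg/dL | Gap |
|---|---|---|---|---|
| Synopsis (4 times), SAP 5.2 (twice) | 54 mg/dL, 2.78 mmol/L | 54/f = 3.00 | 2.78f = 50.09 | 3.91 below 54 |
| 7.2 bolus note | 65 mg/dL, 3.3 mmol/L | 65/f = 3.61 | 3.3f = 59.46 | 5.54 below 65 |
| 7.1 (twice) | 115 mg/dL, 6.83 mmol/L | 115/f = 6.38 | 6.83f = 123.06 | 8.06 above 115 |
| 7.2 item 4 | 0.33 mg/dL·min, 0.002 mM/min | 0.33/f = 0.0183, rounded to 0.02 | 0.002f = 0.036 | 0.33/0.036 = 9.2 times too low |

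**Effect on the dosing window.** The correct window is 54 − 42 = 12.0 mg/dL wide. With 2.78 mmol/L as the upper bound it is 50.09 − 42 = 8.09 mg/dL, narrower by 3.91/12.0 = 32.6%. The narrower window lies wholly inside the correct one and keeps the 42 mg/dL floor.

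**The conflicting reading.** 2.85f = 51.35 mg/dL, which is above 50.09 (restart insulin under the synopsis) and below 54 (inside the dosing range under 7.1).

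**Bolus bands.** Items 3 and 4 bar boluses from 3.39f = 61.08 to 3.61f = 65.05 mg/dL and from 3.00f = 54.05 to 3.33f = 60.00 mg/dL. The prohibition up to 65 mg/dL is therefore stated correctly there, and the note's 3.3 mmol/L disagrees with it.

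**Escalation stop.** 0.15 mg/dL per hour is 0.15/60 = 0.0025 mg/dL per minute, 60 times below the trigger of the same step. The mmol/L figure carries the same slip: 0.008f/60 = 0.0024 mg/dL per minute. Every other rate in the algorithm is per minute.

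**Direction of the two rate slips.** Read literally, 0.002 mM/min would halve the infusion at a much slower glucose fall, and the per-hour stop would end escalation earlier. Both give less insulin, not more.

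**Restart and sampling.** These are differences of text. On the restart rate the synopsis stands alone against 7.1 and a compatible Table 4. On sampling, 7.1 stands alone, though its ±5-minute window around 10 minutes lets a site satisfy both versions.

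**The case against.** The strongest reply is that these are typographical slips whose correct values stand elsewhere.

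- **Governing text.** Protocol 7.3 ties permission to dose to the steady-state criteria in 7.1, which has 54 and 3, and 10.2.1.2 sends insulin adjustments to 7.2 and Table 4. The leading error would bite only if a site followed the synopsis over these. This stands and limits the risk. It does not cover the errors printed in 7.1, 7.2 and Table 4 themselves.
- **The bolus note refers the reader to items 3.b.i and 4.b.i**, which are right. This also stands. But the note is the sentence that limits the investigator's freedom to override the algorithm, so its figure should be right.
- **No site is known to work only in mmol/L.** The correction factor, the SAP bolus formula and the worked readings in 11.2 are in mg/dL. That is fair: the documents show only that mmol/L is allowed.
- **A reading of 2.85 would be rounded up to 2.9** under the 11.2 rule. Since 2.9 × 18.0182 = 52.25 mg/dL is still above 50.09 and below 54, the conflict remains.
- **Aiming near 50 mg/dL was an earlier goal of the algorithm**, as 7.2 says, and the 42 mg/dL floor and termination rules are unchanged. This supports a modest severity, although the current threshold is 54.
- **The 0.002 is one digit and could be a text-extraction artefact.** That cannot be excluded. It is the least weighty item.

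The per-hour stop has no correct counterpart anywhere, because 7.2 and Table 4 both carry it.

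**Conclusion.** The concern holds. Four unit pairs are wrong by the documents' own factor and tables, one time unit is wrong by a factor of 60, and the restart and sampling texts conflict.

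The consequence is a limited conduct and safety risk. A site using 2.78 mmol/L throughout would induce up to 3.9 mg/dL deeper and have a dosing window about one third narrower. No ineligible dosing follows, because that window lies inside the correct one. This assumes a site that works in mmol/L and follows the synopsis. Real-time sponsor monitoring (7.1), the pointer in 11.2 to Tables 4 and 8, and the investigator's power to override the algorithm (except for boluses at or below 65 mg/dL) all reduce the chance of harm. The 6.83 figure loosens the euglycemic limit, but the first bolus is still calculated from measured starting glucose.

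For the analysis, SAP 7.3 standardises glucose to mg/dL, so the slip in SAP 5.2 matters only if its mmol/L figure is programmed. No effect on alpha, power or the treatment comparison is claimed. The errors should be fixed because they steer IV insulin in deliberately hypoglycemic subjects and correction is nearly free.

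**What to change.** - Synopsis (four places) and SAP 5.2 (two places): replace 2.78 with 3.00 mmol/L beside 54 mg/dL.
- Protocol 7.2 bolus note: replace 3.3 with 3.61 mmol/L.
- Protocol 7.1 (two places): replace 6.83 with 6.38 mmol/L.
- Protocol 7.2 item 4: replace 0.002 with 0.02 mM/min.
- Escalation note in 7.2 and Table 4: change per hour to per minute in both units.
- Subject to the sponsor's confirmation of intent, align the synopsis restart rate with 7.1 (120%) and the 7.1 sampling switch with Table 4 (80 mg/dL).
- Send sites a short memo listing the corrected values.

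The cost is wording in the next protocol amendment, two figures in the SAP and one memo. No new data or patients are needed.
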